6.2 DURATION OF STUDY PARTICIPATION

6.2.1 Duration of study participation for each patient

The study comprises 4 periods as described below (please see the graphical study design and study flowchart in Section 1.1 and Section 1.3, respectively):

- A run-in period (if needed) up to 4 weeks (+2 days) in duration.
- A screening period up to 2 weeks (+5 days) in duration.
- A double-blind treatment Period 24 weeks in duration.
- A 80-week open label treatment period.

The total duration of the study will be up to 110 weeks for each patient.

A detailed description of the assessments performed in each study period is provided in Section 10.1.

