9.2.4.1 Observation period

The observation of safety data will be as follows:

- Pre-treatment period: The Pre-treatment observation period is defined from the signed informed consent up to the first dose of double-blind IMP.
- Double-blind treatment-emergent adverse event (TEAE) period: The double-blind TEAE observation period is defined as the time from the first dose of double-blind IMP to the last dose of double-blind IMP injection +70 days (10 weeks) for those patients not proceeding into the open label treatment period as residual effect of alirocumab is possible until 10 weeks after the stop of treatment IMP injection, or up to the day before first dose of open label IMP for those patients proceeding into the open label treatment period.
- Open label TEAE period: The open label TEAE observation period is defined as the time from the first dose of open label IMP to the last dose of open label IMP injection +70 days (10 weeks).
- Post-treatment period: The post-treatment observation period is defined as the time starting the day after the end of the double-blind and open label TEAE periods up to the end of the study for each patient.

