10.4.3 General guidelines for reporting adverse events

All AEs, regardless of seriousness or relationship to IMP, spanning from the signature of the informed consent form until the end of the study as defined by the protocol for that patient, are to be recorded on the corresponding page(s) or screen(s) of the e-CRF.

Whenever possible, diagnosis or single syndrome should be reported instead of symptoms. The Investigator should specify the date of onset, intensity, action taken with respect to IMP, corrective treatment/therapy given, additional investigations performed, outcome, and his/her opinion as to whether there is a reasonable possibility that the AE was caused by the IMP.

Laboratory, vital signs are to be recorded as AEs only if:

- Symptomatic and/or
- Requiring either corrective treatment or consultation, and/or
- Leading to IMP discontinuation or modification of dosing, and/or
- Fulfilling a seriousness criterion, and/or
- Defined as an AE of special interest with immediate notification.

The Investigator should take appropriate measures to follow all AEs until clinical recovery is complete and laboratory results have returned to normal, or until progression has been stabilized, or until death, in order to ensure the safety of the patients. This may imply that observations will continue beyond the last planned visit per protocol, and that additional investigations may be requested by the monitoring team up to as noticed by the Sponsor. At the prespecified study end-date, patients who experience an ongoing SAE or an AESI should be followed until resolution, stabilization, or death and related data will be collected.

When treatment is prematurely discontinued, the patient's observations will continue until the end of the study as defined by the protocol for that patient.

Instructions for AE reporting are summarized in Table 2 and in Appendix F.

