2.1.4 Safety endpoints

The safety analysis will be based on the reported AEs and other safety information, such as clinical laboratory data, vital signs, Tanner stage and Cogstate battery (neurocognitive functions) test assessment.

Observation period for the Q2W dosing regimen cohort,

The observation of safety data will be as follows:

- The pre-treatment period is defined from the signed informed consent up to the first dose of double-blind IMP.
- Double-blind treatment-emergent adverse event (TEAE) period is defined as:
 - the time from the first dose of double-blind IMP to the last dose of double-blind IMP injection +70 days (10 weeks) as residual effect of alirocumab is possible until 10 weeks after the stop of treatment IMP injection. This period will be truncated at the first dose of open-label IMP for patients proceeding into the OL treatment period.

The double-blind TEAE period will include:

- The double-blind treatment period defined as the time from the first dose of doubleblind IMP injection up to the day of last dose of double-blind IMP injection +21 days.
- The double-blind post-treatment period is defined as the time starting the day after the end of the double-blind TEAE period (truncated at the first dose of open-label IMP for patients proceeding into the open-label treatment period).
- The open-label TEAE period is defined as the time from the first dose of open-label IMP injection up to the day of last dose of open-label IMP injection +70 days.
 - The open-label TEAE period will include the open-label treatment period defined as the time from the first dose of open-label IMP injection up to the day of last dose of open-label IMP injection + 21 days.
- The open-label post-treatment period is defined as the time starting the day after the end of the open-label TEAE period (ie, 71 days after the day of last dose of open-label IMP injection).

Observation period for the Q4W dosing regimen cohort,

The observation of safety data will be as follows:

- The pre-treatment period is defined from the signed informed consent up to the first dose of double-blind IMP.

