• The event rate per patient year (the number of patients with an event in question divided by total patient-years) will be provided for all TEAEs by SOC and PT. For a patient with event, patient year is censored at time of first event; for patient without event, it corresponds to length of the open-label TEAE period

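### Open-label adverse-event rates give each event-free completer 6 to 8 weeks of person-time after AE collection has ended, so the rates are understated

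*SAP*

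**What the plan says.** SAP 2.4.5.1 adds a rate table for the open-label period, for all TEAEs by SOC and PT: patients with the event divided by total patient-years. The person-time rule has two parts. "For a patient with event, patient year is censored at time of first event", and "for patient without event, it corresponds to length of the open-label TEAE period".

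SAP 2.1.4 defines the open-label TEAE period identically in both cohorts, as "the time from the first dose of open-label IMP injection up to the day of last dose of open-label IMP injection +70 days". Protocol 9.2.4.1 agrees: "the time from the first dose of open label IMP to the last dose of open label IMP injection +70 days". Neither caps it at the last visit, last contact or end of study.

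AE recording has a different end. Protocol 10.4.3 has AEs recorded over a window "spanning from the signature of the informed consent form until the end of the study as defined by the protocol for that patient", and SAP 2.1.4.1 likewise stops at end of study. Protocol 6.2.1 states: "The total duration of the study will be up to 110 weeks for each patient". The flow chart (Protocol 1.3) ends at Week 104. The Week 104 visit (Protocol 10.1.4.7) closes open-label treatment and lists neither an injection nor a kit dispensation.

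**The concern.** A rate per patient-year is interpretable only if the denominator counts time in which an event would have entered the numerator. Here the denominator follows a drug-exposure window (last dose plus 70 days) and the numerator follows the data-collection window (to end of study). For a patient who completes treatment, the first extends beyond the second, and the difference is counted as event-free although nobody was systematically asking about new events.

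Protocol 9.2.4.1 shows the same mismatch. It starts the post-treatment period the day after the TEAE period and ends it at the patient's end of study. For a completer the start falls after the end.

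This is the only per-patient-year AE rate in the SAP. It covers the long-term exposure period of a paediatric trial whose sample size was raised specifically for safety assessment (Protocol 11.1). The bias lowers every SOC and PT rate, and it differs slightly between regimens.

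**Working it through.** **Inputs**

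- Open-label period: 80 weeks, Week 24 to Week 104 (Protocol 6.2.1, 8.1).
- Injection every 2 or 4 weeks from Week 24, none listed at Week 104 (Protocol 8.1, 10.1.4.7).
- TEAE tail: 70 days = 10 weeks (SAP 2.1.4; Protocol 9.2.4.1).
- AE recording ends at the patient's end of study (Protocol 10.4.3; SAP 2.1.4.1), taken here as Week 104.

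**Is there room for follow-up in the stated duration?** Run-in 4 + screening 2 + double-blind 24 + open-label 80 = 110 weeks. This reproduces the stated total exactly and leaves no post-treatment follow-up. The documents give no open-label event rate, so there is none to reproduce.

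**Person-time of an event-free completer**

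| | Q2W | Q4W |
|---|---|---|
| Nominal last injection | Week 102 | Week 100 |
| TEAE period ends (+10 weeks) | Week 112 | Week 110 |
| Weeks past Week 104 | 112 − 104 = 8 | 110 − 104 = 6 |
| Weeks counted from Week 24 | 88 | 86 |
| Weeks observed | 80 | 80 |
| Counted / observed | 88/80 = 1.100 | 86/80 = 1.075 |
| Maximum understatement of the rate | 1 − 80/88 = 9.1% | 1 − 80/86 = 7.0% |

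A Q4W patient adjusted to Q2W dosing falls in the Q2W column. With the ±7-day window on the Week 104 visit, the excess is 7 to 9 weeks (Q2W) or 5 to 7 weeks (Q4W).

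**Dependence on event frequency.** Only event-free patients carry the excess. Assume a constant hazard λ per week and that all patients complete. Let p = 1 − exp(−80λ) be the 80-week incidence and x the excess (8 or 6 weeks). Then, per patient:

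- observed person-time = p/λ
- SAP person-time = p/λ + (1 − p)x
- understatement = 1 − observed/SAP

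For p = 5%: λ = −ln(0.95)/80 = 0.000641, so p/λ = 77.98 weeks. The SAP denominator is 77.98 + 0.95 × 8 = 85.58 (Q2W) or 77.98 + 0.95 × 6 = 83.68 (Q4W). The rate per 100 patient-years is 3.35 on observed time, against 3.05 (Q2W) or 3.12 (Q4W) under the SAP rule.

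| Assumed 80-week incidence | Understatement, Q2W | Understatement, Q4W |
|---|---|---|
| near 0 (limit) | 9.1% | 7.0% |
| 5% | 8.9% | 6.8% |
| 20% | 8.2% | 6.3% |
| 50% | 6.5% | 4.9% |
| 80% | 3.9% | 2.9% |

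**Scale.** The plan expects about 128 patients with two years of safety assessment (Protocol 11.1). If they split evenly between cohorts and all were free of a given event, the unobserved time would be 64 × 8 + 64 × 6 = 896 weeks, about 17 patient-years. The observed time would be 128 × 80 = 10,240 weeks, about 196 patient-years.

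**The case against.** The strongest objection is that no passage says outright that AE collection stops at Week 104. Protocol 9.2.4.2 refers to Section 6.2.2 for a per-patient end of study, but that section defines only the trial-wide end. Protocol 8.8.3 mentions a follow-up visit, and Protocol 8.2 an additional open-label period. This wording is loose and needs reconciling. None of it sets up AE collection for 70 days after the last dose: no such visit is scheduled, the additional period has no visit schedule, and Protocol 10.4.3 ties recording to the individual patient's end of study. If dosing did run past 80 weeks, the figures above would change, but the tail after the last dose would still be uncovered.

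Capture after Week 104 is also not strictly nil. Protocol 10.4.3 continues follow-up of existing AEs, and Protocol 10.4.4 asks for SAEs judged related that come to the investigator's attention later. That stands, but it is not systematic collection of new AEs, and this table covers all TEAEs.

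SAP Section 3 does end the open-label TEAE period at the cut-off date, but only at the first-step analysis and only for patients still ongoing. Completers and the final analysis are not covered.

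Residual drug effect is the reason given for the 70 days. It justifies attributing an observed event to treatment. It does not justify counting unobserved time as event-free.

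Finally, the effect is modest, the rates are descriptive, the open-label period has no control group, and the main AE tables use counts and percentages without person-time. All of that is correct and limits the importance of the point. Patients who stop at least 10 weeks before Week 104 and stay in the study carry no excess.

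**Conclusion.** The concern holds. Applied as written, the rule gives every event-free completer about 8 weeks (Q2W) or 6 weeks (Q4W) of person-time after scheduled AE collection has ended. Rates are understated by at most 9.1% and 7.0% respectively, near those limits for uncommon events and by about half as much or less at 80% incidence.

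The figures assume nominal dosing with the last injection one interval before Week 104, AE collection ending at the Week 104 visit, and, for the incidence table, a constant hazard with all patients completing. The conclusion that the denominator is too large needs only that collection ends before last dose plus 70 days. Primary and key secondary efficacy inference is untouched. This should be corrected before the final open-label analysis, but it does not threaten the trial's main conclusions.

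**What to change.** In SAP 2.4.5.1, replace the person-time rule for this table: person-time starts at the first open-label dose and ends at the earliest of the first event, the last open-label dose plus 70 days, and the patient's end of study or last contact. Apply the same cap wherever else the length of the TEAE period serves as time at risk. For the first-step analysis, keep the existing cut-off rule for ongoing patients and apply the cap to those who have already finished. The 70-day window for classifying an observed AE as treatment-emergent need not change.

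The per-patient end of study should also be defined explicitly, so that Protocol 6.2.2, 8.2, 8.8.3 and 9.2.4.2 agree on when AE collection stops.

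The cost is one sentence in the SAP. The date of last contact is already used in SAP 2.5.3, so no new data are needed. Reported rates would rise by up to 10.0% (Q2W) or 7.5% (Q4W) relative to those under the current rule.

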2.4.5.2 Deaths

The following summaries of deaths will be generated separately for double-blind and OL periods:

- Number (%) of patients from the safety population who died by period (on-treatment, post-treatment).
- TEAEs leading to death (death as an outcome on the AE as reported by the Investigator) by primary SOC, HLGT, HLT, and PT sorted by internationally agreed SOC order, with HLGT, HLT, and PT presented in alphabetical order within each SOC. TEAEs leading to death are TEAEs that led to death regardless of timing of death in relation to IMP injection (ie, death occurring in the TEAE period or during the post-treatment period).
- In addition, deaths in nonrandomized patients or randomized but not treated patients will be summarized.

2.4.5.3 Analyses of laboratory variables

The summary statistics (including number, mean, median, Q1, Q3, SD, minimum and maximum) of all laboratory variables (central laboratory values and changes from baseline) will be calculated for each visit or study assessment (baseline, each post-baseline value of the treatment period, last on-treatment and worst on-treatment value). In addition, for some parameters of interest, mean changes from baseline with the corresponding SE could be plotted over time (at same time points). This section will be organized by biological function as specified in Section 2.1.4.3. For glucose, only fasting samples will be summarized.

The incidence of PCSAs (list provided in Appendix A and Appendix B), as well as ALT increase as defined as AESI, at any time during the TEAE period will be summarized by biological function irrespective of the baseline level and/or according to the following baseline status categories:

- Normal/missing
- Abnormal according to PCSA criterion or criteria

For laboratory parameters for which PCSA criterion is not defined, similar table(s) using the normal range could be provided.

For clinical laboratory parameters during the OL period, summary tables as described for the double-blind period above will be used with the exceptions of the analyses by visit (unless data warrants further investigation)

Drug-induced liver injury

The liver function tests, namely AST, ALT, ALP, and total bilirubin, are used to assess possible drug-induced liver toxicity. The proportion of patients with PCSA values or ALT increase as defined in the section grouping of adverse events (see Section 2.1.4.1) during TEAE period by baseline status will be displayed for each parameter.

An evaluation of drug-induced serious hepatotoxicity (eDISH) with the graph of distribution of peak values of ALT versus peak values of total bilirubin will also be presented using post-baseline values during TEAE period. Note that the ALT and total bilirubin values are presented on a logarithmic scale. The graph will be divided into 4 quadrants with a vertical line corresponding to 3 x ULN for ALT and a horizontal line corresponding to 2 x ULN for total bilirubin.

Listing of possible Hy's law cases identified by treatment group (ie, patients with any elevated ALT>3 x ULN, and associated with an increase in bilirubin >2 x ULN, concomitantly or not) with ALT, AST, ALP, total bilirubin, and if available direct and indirect bilirubin will be provided.

The incidence of liver related TEAEs will be summarized. The selection of PTs will be based on SMQ Hepatic disorder (see Section 2.1.4.1).

Gonadal hormones and pituitary hormones

Girls and boys will be described separately.

• For girls

The following analyses will be provided only in post-menarchal girls for at least 1 year at baseline and without receiving any oral contraceptive throughout the study.

- Changes from baseline will be tabulated by time point for estradiol and pituitary hormones (FSH and LH) during treatment period.
- Similar table as for PCSA will be provided using normal range during the TEAE period. The number (%) of patients with at least one estradiol value <LLN and LH >ULN, estradiol value<LLN and FSH >ULN, estradiol value <LLN and LH>ULN and FSH >ULN) during the TEAE period will be presented.

In addition, a listing of estradiol, LH, FSH values over time along with the tanner stage and date of last menses (if any) will be displayed for all girls.

• For boys

The following analyses will be provided only in boys with at least a Tanner stage 2

- Changes from baseline will be tabulated by time point for testosterone and pituitary hormones (FSH and LH) during treatment period.
- Similar table as for PCSA will be provided using the normal range. The number (%) of patients with at least one testosterone value <LLN and LH >ULN, testosterone

value<LLN and FSH >ULN, testosterone value<LLN and LH>ULN and FSH >ULN) during the TEAE period will be presented.

In addition, a listing of testosterone, LH, FSH values over time along with the tanner stage will be displayed for all boys.

Adrenal gland hormones

DHEAS:

Girls and boys will be described separately.

- Changes from baseline will be tabulated by time point.
- Similar table as for PCSA will be provided using the normal range during the TEAE period.

These summaries will be provided in post-menarchal girls for at least 1 year at baseline and without receiving any oral contraceptive throughout the study, and in boys with at least a tanner stage 2.

In addition, a listing of all values over time along with normal range will be provided.

Cortisol and ACTH

Girls and boys will be analyzed together. Samples not drawn between \geq 6:00 AM and <11:00 AM will be excluded.

- Changes from baseline will be tabulated by time point for cortisol during treatment period.
- Similar table as for PCSA will be provided using the normal range during the TEAE period. The number (%) of patients with at least one cortisol <LLN, cortisol <LLN and ACTH >ULN will be presented.

Although the summaries for gonadal and pituitary hormones and DHEA will be provided as planned for safety endpoints (ie, by treatment groups within each dosing regimen cohort, and by treatment groups regardless of the dosing regimen cohorts), the analyses by treatment regardless of the dosing regimen cohorts (ie, pooled across the cohorts) appears the most relevant, due to the restriction of the population involved in those analyses (post-menarchal girls for at least 1 year at baseline and without receiving any oral contraceptive throughout the study, and in boys with at least a tanner stage 2).

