8.8.2 Contraception

Females of childbearing potential must use an effective contraceptive method throughout the entire duration of the study treatment (including the double-blind treatment period and the open label treatment period) and for at least 10 weeks after the last IMP injection (see Appendix D).

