1.1 STUDY DESIGN AND RANDOMIZATION

This study is a randomized, 24-week double-blind, placebo-controlled, parallel-group, multinational, multi-center study followed by an open-label treatment period of 80 weeks.

Approximately 150 children and adolescents 8 to 17 years of age with heterozygous familial hypercholesterolemia (heFH) and low-density lipoprotein cholesterol (LDL-C) \geq 130 mg/dL (3.37 mmol/L) at the screening visit, despite stable lipid modifying therapies (LMTs), are randomized to alirocumab or placebo using a 2:1 ratio (alirocumab: placebo). Two dosing regimens, administration every 2 weeks (Q2W) and every 4 weeks (Q4W), will be evaluated with approximately 75 patients in each dosing regimen cohort. Recruitment in the Q4W dosing regimen cohort started once recruitment in the Q2W dosing regimen cohort was completed and the protocol amendment was approved.

A Flow Mediated Dilation (FMD) exploratory sub-study is also planned to involve a subset of 30-39 patients at selected sites.

Note: Patients who had previously participated in the DFI14223 study and had received alirocumab administration during the open-label extension of the DFI14223 study required a wash-out period of at least 10 weeks between the last injection of alirocumab and the screening lipid assessment at the entry of the screening period. However, as these patients had already met the LDL-C requirement of at least 130 mg/dL (3.37 mmol/L) when they were screened for the DFI14223 study, they were not excluded based on the LDL-C value obtained during the screening for the EFC14643 study.

Randomization is stratified according to previous participation (yes or no) in the Phase 2 DFI14223 study and baseline body weight (BW) (<50 or ≥ 50 kg).

The study is comprised of 4 periods as described below:

- A run-in period (if needed) up to 4 weeks (+2 days) in duration.
- A screening period up to 2 weeks (+5 days) in duration.
- A 24-week double-blind treatment period.
- A 80-week open-label treatment period.

The total study duration may be up to 110 weeks (+7 days).

Double-blind treatment period:

Two dosing regimens will be evaluated, Q2W and Q4W. Patients will be included in them in a sequential manner, ie, the first half of the patients in the Q2W dosing regimen cohort then the second half of patients in the Q4W dosing regimen cohort. Patients will be blinded to study treatment and randomized to either alirocumab or placebo using a 2:1 ratio for each dosing regimen cohort.

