2.1.4.3 Laboratory safety variables

Clinical laboratory data consist of blood analysis, including hematology and clinical chemistry. Clinical laboratory values will be analyzed into international units. International units will be used in all listings and tables. Clinical laboratory values converted into conventional (US) units will be also available in the database. Analyses can be provided upon request.

Unless otherwise specified below, blood samples for clinical laboratories (eg, hematology, clinical chemistry) were to be collected during:

- Screening at Visit 2 (up to Week -2).
- The double-blind period at Visit 4 (Week 0 / Day 1), Visit 6 (Week 12) and Visit 7 (Week 24) /or early termination.
- The OL period at Visit 8 (Week 32), Visit 9 (Week 44), Visit 11 (Week 68) and Visit 14 (Week 104)/or early termination, for patients proceeding into OL period.

Adrenal gland hormones, gonadal and pituitary hormones, fat soluble vitamins, were to be collected during:

- The double-blind period at Visit 4 (Week 0 / Day 1) and Visit 7 (Week 24)/or early termination
- The OL period at Visit 9 (Week 44), Visit 11 (Week 68) and Visit 14 (Week 104)/or early termination, for patients proceeding into OL period.

The following laboratory parameters (excluding those considered as efficacy parameters) will be classified as follows:

- Hematology:
 - Red blood cells and platelets: hemoglobin, hematocrit, red blood cell count, platelet count and hematocrit
 - White blood cells: white blood cell count, neutrophils, lymphocytes, monocytes, basophils, eosinophils.
- Clinical chemistry:
 - Metabolism: glucose, total protein, albumin, creatine phosphokinase (CPK),
 - Electrolytes: sodium, potassium, chloride, calcium, phosphorus, bicarbonate,
 - Renal function: creatinine, eGFR, creatinine clearance, blood urea nitrogen, uric acid,
 - Liver function: alanine aminotransferase (ALT), aspartate aminotransferase (AST), alkaline phosphatase (ALP), gamma glutamyl transferase (γGT), lactate dehydrogenase (LDH), total bilirubin, and in case of total bilirubin values above the normal range, must include conjugated and non-conjugated bilirubin (used for describing individual cases only).
- Adrenal gland hormones: cortisol (with reflexive adrenocorticotrophic hormone (ACTH) levels if cortisol < lower limit of normal [LLN]) and dehydroepiandrosterone sulfate (DHEAS).
- Gonadal hormones: testosterone (males) and estradiol (females).

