3 INTERIM ANALYSIS

The analyses will be conducted in 2 steps. The first analysis will not be conducted before completion of the double-blind treatment period. Since analysis of double-blind primary and key secondary efficacy endpoints will have been concluded at the time of the first step analysis described below, no multiplicity adjustment for multiple analyses is needed (see Section 2.4.4.3), and the overall significance level remains at 0.05 for the study.

- First step analysis: Analysis of the completed double-blind treatment period and first step analysis of the open-label treatment period
 - This analysis will be conducted when all patients have been randomized and have at least all their lipid data up to Week 24 analysis window (double-blind period) collected and validated.
 - The efficacy analyses of the double-blind period will consist in the final analysis of the primary and secondary efficacy endpoints (except those measured during open-label period). Analysis of lipid data collected during the OL period will be descriptive.
 - The safety analyses of the double-blind period will not be fully final at the time of this analysis since the double-blind TEAE period will be truncated at the cut-off date for some patients. The safety analyses of the double-blind and open-label treatment periods will be performed on all safety data collected up to the common cut-off date. The common cut-off date is defined as date of the last patient included completed Week 24 visit.
- Final analysis of the open-label treatment period
 - This analysis will be conducted at the end of the study with the data of the open-label treatment period and will consist in the final analysis of the safety and efficacy measures of the open-label treatment period.

Analyses methods and conventions described in the other sections of this SAP will be applied for all analyses as applicable. The following additional rules will apply for analyses performed at first analysis:

- Any lipid assessments within analysis windows up to Week 24 will be taken into account (may include few unscheduled lipid data soon after the cut-off date).
- Open-label period: Patients without end of treatment visit performed at the time of the cutoff date will be considered as ongoing and exposed up to the cut-off date. Therefore:
 - Patients who did not complete treatment period nor prematurely discontinued the study treatment at cut-off date will be analyzed as "ongoing" in the disposition summary.

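### SAP 2.4.5.3 drops a girl from all estradiol, LH, FSH and DHEAS summaries if she takes an oral contraceptive at any time in the study, discarding contraceptive-free double-blind values

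*SAP*

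**What the plan says.** For girls, the SAP provides changes from baseline in estradiol, LH and FSH, out-of-range counts, and counts of low estradiol combined with high LH and/or FSH. These analyses "will be provided only in post-menarchal girls for at least 1 year at baseline and without receiving any oral contraceptive throughout the study". The DHEAS paragraph repeats the rule: "These summaries will be provided in post-menarchal girls for at least 1 year at baseline and without receiving any oral contraceptive throughout the study". The section ends by restating the restriction and concluding that, because of it, "the analyses by treatment regardless of the dosing regimen cohorts (ie, pooled across the cohorts) appears the most relevant".

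For girls left out of the summaries, the SAP keeps individual listings. Estradiol, LH and FSH values are listed with Tanner stage, and "date of last menses (if any) will be displayed for all girls". All DHEAS values are listed with the normal range.

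In the placebo-controlled part of the trial these hormones are sampled only twice: "The double-blind period at Visit 4 (Week 0 / Day 1) and Visit 7 (Week 24)/or early termination" (SAP 2.1.4.3).

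**The concern.** The two conditions in the population rule are of different kinds. Time since menarche is fixed at baseline. Oral contraceptive use is judged over the whole study, which includes 80 weeks of open-label treatment after the 24-week double-blind period. Nothing restricts it to the period being summarised, and nothing retains values taken before the contraceptive was started.

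There is a good reason to leave out hormone values taken on an oral contraceptive. That reason does not reach values taken before it. At stake is the placebo-controlled summary of endocrine safety in adolescent girls. It loses usable data, and inclusion depends on what happens after the comparison is over, when both arms are receiving alirocumab.

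New starts are foreseeable. Protocol 8.8.2 requires that "Females of childbearing potential must use an effective contraceptive method throughout the entire duration of the study treatment", and Protocol Appendix D lists combined and progestogen-only oral methods among those accepted.

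**Working it through.** The plan gives no figure to reproduce here, so the check sets the rules side by side and then shows assumed ranges.

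**1. Can an open-label start affect a double-blind value?** SAP 2.1.4 truncates the double-blind TEAE period at the first open-label dose for patients who continue. The double-blind hormone values are Week 0 and Week 24. An oral contraceptive started after that first open-label dose cannot influence either. SAP 2.4.5.3 nevertheless removes the girl from every summary, including the double-blind ones.

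**2. How far ahead does the rule look?** Under SAP section 3, "The safety analyses of the double-blind and open-label treatment periods will be performed on all safety data collected up to the common cut-off date", and medications after the cut-off are not included. The cut-off is the last included patient's Week 24 visit. At the first-step analysis a continuing girl's look-ahead is therefore at most

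min(80 weeks, time from her Week 24 visit to the cut-off).

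For the last patient this is zero. Q4W recruitment began once Q2W recruitment was complete (SAP 1.1), so it is generally longer for Q2W girls. Enrolment dates are not given, so no length can be calculated.

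**3. How many girls?** The documents give neither the number of eligible girls nor the rate of starting. Assume that 15% to 35% of the planned 100 alirocumab and 50 placebo patients are eligible girls, and that 5% to 20% of these start an oral contraceptive:

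- Low end: 100 × 0.15 × 0.05 = 0.75 alirocumab and 50 × 0.15 × 0.05 = 0.375 placebo, about 1 girl in all.
- High end: 100 × 0.35 × 0.20 = 7 alirocumab and 50 × 0.35 × 0.20 = 3.5 placebo, about 10 girls in all.

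These counts include girls who start before Week 24. The number with a fully contraceptive-free double-blind record is smaller.

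**4. What if starting depends on the hormone value?** Suppose, purely for illustration, that Week 24 estradiol change is normal with SD 1, that alirocumab shifts it by −0.5 SD, and that low means below −1 SD. The low share p is Φ(−0.5) = 30.9% on alirocumab and Φ(−1) = 15.9% on placebo, a gap of 15.0 points. If low girls start with probability h and others with probability 5%, the low share among girls kept is

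p(1 − h) / [p(1 − h) + (1 − p)(0.95)].

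| h | Alirocumab | Placebo | Gap |
|---|---|---|---|
| 30% | 0.216/0.873 = 24.7% | 0.111/0.910 = 12.2% | 12.5 points |
| 60% | 0.123/0.780 = 15.8% | 0.063/0.863 = 7.4% | 8.5 points |

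In simulation with the same inputs, the mean difference moves from −0.50 SD to −0.47 (h = 30%) and −0.41 (h = 60%). With the same 10% start rate whatever the value, it stays at −0.50. With no true shift it stays at 0. The possible effect is dilution of a real difference; no spurious one appears when the arms follow the same starting pattern.

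**The case against.** Much of the case against reading more into this stands.

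- **Bias.** A reader might infer that the arms are no longer comparable because girls with hormonal problems are selectively removed. The documents do not say why a contraceptive would be started. The reason they do give, required contraception, may be unrelated to arm or hormone level, and then only data are lost. After Week 24 both arms receive alirocumab, so only effects already present by then could separate them.
- **Size.** A reader might take 80/104 = 77% as the share of removed girls with fully valid double-blind data. That needs starts spread evenly over 104 weeks and double-blind tables re-run at study end. The first-step analysis ignores later medication, and section 3 describes the second step as the final open-label analysis. Exclusion E30 also requires females of childbearing potential to be protected at entry, so many users may already be on an oral contraceptive at baseline and would be excluded under either rule. The 77% is at most an upper-end illustration.
- **Cohorts.** The longer Q2W look-ahead might suggest treatment bias. It applies to both Q2W arms, and allocation is 2:1 in each cohort, so it creates none by itself.
- **Visibility.** The tables are descriptive and use the as-treated safety population (SAP 2.3.2, 2.4.5). Individual values are listed, and adverse events are tabulated without the contraceptive exclusion.

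None of this supplies a reason to discard values taken before a contraceptive was started. A listing is also not a between-arm summary.

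**Conclusion.** As written, the rule removes contraceptive-free Week 0 and Week 24 values from the double-blind girls' hormone tables because of later events. A programmer following the text would implement it that way, even if a period-specific rule was intended. What can be asserted is a needless loss from a subgroup the SAP itself treats as restricted, and inclusion that depends on events after the double-blind period. Dilution of a real difference is possible only if starting is related to hormone levels, which the documents do not establish. The number affected is unknown; the range of about 1 to 10 rests entirely on the assumed shares above. No efficacy or inferential result is affected. The change is worth making because it is cheap and concerns paediatric endocrine safety.

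**What to change.** In SAP 2.4.5.3, for estradiol, LH, FSH and DHEAS, exclude at patient level only girls taking an oral contraceptive at baseline. For girls who start later, keep hormone values up to the day before the start and exclude values from that date on. Apply this separately to the double-blind and open-label summaries, and carry it into the closing paragraph on the pooled analyses. Report by arm how many girls were excluded at baseline and how many started before Week 24.

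The cost is a wording change and a date filter on concomitant medication data already collected. SAP 2.1.2 already defines concomitant medication by period, and 2.4.5.3 already excludes single samples elsewhere (cortisol by time of draw, non-fasting glucose). A line on incomplete start dates is needed, because SAP 2.5.3 does not impute medication dates.

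There are two limits. The number of girls will vary by visit. Girls who start before their Week 24 sample still contribute no double-blind change value, which is why their number by arm should be shown.
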